## 6.2 Timeline Flowchart

### **6.3 Recruitment**

We will mail a randomly selected sample of adults aged 25 years and over registered with participating general practices in the study areas.

The Scottish Primary Care Research Network (SPCRN) will be involved in recruitment of patients to this study from primary care. SPCRN staff provide GP practices with an expert service to undertake searches of their electronic databases to identify a random sample of potentially eligible patients and prepare the ethically approved letters to be sent out. SPCRN staff work on behalf of the healthcare team under practice staff supervision. Each member of SPCRN staff must have a current NHS substantive or honorary contract in order to carry out these activities. Searches are undertaken at each GP practice before the screening survey questionnaires are sent out by Health Informatics Centre Services in Dundee on behalf of the practice. Patients will return completed survey questionnaires to the research team at the University of Aberdeen where they will be assessed by the research team for eligibility and sent invitation letters if eligible.

The “screening questionnaire” will determine whether a) they meet the study eligibility criteria and b) they would be willing to be contacted again regarding a treatment trial for “musculoskeletal health”. The questionnaire will include:

- Pain assessed by specific questions on the experience of pain, consultation and body manikins (which will provide site and also allow us to exclude those who already have chronic widespread pain).
- Illness Behaviour Scale (18)
- Somatic Symptoms Scale (excluding pain items) (19)
- Sleep Problem Scale (20)
- Quality of Life and Wellbeing (EQ-5D-5L (21); ICECAP (22))
- General Health Questionnaire (23)
- Chalder Fatigue Scale (24)

The inclusion criteria are:

- A ‘high-risk’ profile for developing CWP as identified on the screening survey, i.e.:
  - Have pain for which they have sought consultation to primary care in the last 6 months, or have pain and report consulting a doctor frequently
  - Any 2 of the following:
    - Illness Behaviour Score > 4
    - Somatic Symptom Score > 2
    - Sleep Problem Score >= 4
- Access to a landline telephone or mobile telephone

- Ability to understand English sufficiently to participate in the intervention
- Ability to give informed consent
- Aged 25 years or over

Exclusion criteria:

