1.4. SAMPLE SIZE CALCULATIONS

Our previous longitudinal study of onset of CWP (and subsequent replication) has suggested that 21% of "high risk" persons identified will develop CWP over the course of the next twelve months. Our previous data is based on persons with pain and at least 2 out of 3 other "risk factors". There are no published studies of prevention of CWP on which to base our measure of effect. However in the MUSICIAN study some subjects, although reporting CWP at the screening survey, no longer had CWP at the enrolment interview. They were however still eligible to take part, provided they had regional pain. Therefore those subjects with regional pain provide a sub-population on which to base the likely effects of the tCBT. Amongst such subjects, those who received tCBT had a reduced odds of having CWP at the end of the study OR 0.5 95% CI (0.2-1.4) compared to those in usual care.

Thus the study is powered on the ability of the current study to reduce the onset of CWP from 21% to 12%, with 90% power and a 5% significance level. We further assume, based on prior data, that 75% of persons allocated to the tCBT arm will be adherent to the intervention, and that 80% of all subjects will return the follow-up questionnaires to assess outcome.

Final Sample Size

Accordingly we require 473 subjects per arm that is a total of 946 subjects recruited. In MUSICIAN exactly 50% of those found eligible and willing to consider taking part ultimately were randomised. A previous trial of a cognitive-behavioural intervention to prevent chronic pain found that 36% of patients identified as eligible ended up being recruited to the study. If 80% of eligible patients agreed to be contacted about taking part, this equates to 45% of those eligible and willing to consider taking part being randomised - higher numbers for a clinical trial of CWP reflect the fact that this is a prevention trial rather than a treatment trial and may be less attractive to potential participants. Thus we aim to find a total of 2102 subjects who are eligible and willing to consider taking part. Assuming a participation rate to the survey of 30%, that 1 in 4 people will be "at risk", and (using data from MUSICIAN) that 80% of people who return a questionnaire agree to consider taking part, we require to survey 35,037 persons.

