2.4. ANALYSIS

2.4.1.GENERAL PRINCIPLES

For the equivalence study, the adjusted mixed model ITT analysis will be deemed the primary analysis with an adjusted mixed model per protocol analysis as a sensitivity analysis. For the superiority study, in accordance with CONSORT guidelines, all comparative analysis will be conducted on an ITT mixed model basis with a per protocol mixed model analysis performed as a sensitivity analysis. All analyses will be governed by this comprehensive SAP which will be agreed by the Trial Steering Committee (TSC) prior to any analyses being undertaken. There will be no formal interim analyses undertaken. Unless otherwise specified, a 5% two-sided significance level will be used to denote statistical significance. Adjustments will be made for multiple testing of secondary outcomes as discussed below.

2.4.2.DATA DESCRIPTION

Characteristics of the study participants in the two treatment arms will be described using simple summary statistics for each treatment group separately and for all participants together. Descriptive statistics will include mean and standard deviation for normally distributed continuous data, median and inter-quartile range for skewed continuous data and count and percentage for categorical data. No formal statistical comparisons will be made between baseline characteristics. Outcomes will be described at the three follow-up times: 3, 12 and 24 months, using appropriate summary statistics.

2.4.3.FLOW DIAGRAM

A CONSORT flow diagram will provide the detail of the flow of trial participants, withdrawals and post-randomisation exclusions.

2.4.4.ANALYSIS OF PRIMARY OUTCOME

Primary outcome study

The primary outcome is the between arm difference in the proportions of participants developing CWP from baseline to 12 months. This comparison will be made using simple chi-squared tests at each follow-up time. Appropriate adjustment will be made for the stratification factor used in the randomisation (the number of non-pain “high-risk” factors that a participant reports at baseline) using multiple logistic regression.

The model for outcome CWP (yes or no at 12 months) will be a multiple logistic regression. The key adjustments will be for the blocking factors, the number of high-risk factors present (2 or 3 of illness behaviour score >4, somatic symptom score >2 and sleep problem score >4) and GP practice.

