$\text{Logit}(p(\text{CWP})) = \text{constant} + \text{treatment effect} + \text{blocking effect} + \text{other covariate effects} + \text{random error}.$

The treatment effect will be a fixed effect. The blocking effect will comprise the number of high-risk factors present (fixed effect) and GP practice (random effect, n=16 practices).

The other covariates that will be considered in the model are: age and sex. The expectation is that these covariates will be balanced through randomisation, but they are both known to be related to the likelihood of the development of CWP. Multiple imputation (MI) analysis will be used to examine sensitivity to missing data.

After discussion at the TSC it was decided that it will not be possible to consider the therapist effect in a formal way between the two arms. Only one arm will be exposed to the therapists and even descriptive approach was disregarded as the number of participants was expected to vary widely between different therapists.

2.4.5.ANALYSIS OF SECONDARY OUTCOMES

Secondary outcomes

Comparisons with appropriate hypothesis tests will be used for the secondary outcomes, pain, illness behaviour, somatic symptom reporting, sleep problems, quality of life and wellbeing, psychological distress, patient global impression of change measure and fatigue. Appropriate adjustment will be made for the stratification factor. The baseline value of the relevant outcome variable will also be included as a covariate. Given the multiple secondary outcomes, the p-value used to denote statistical significance will reflect the multiple comparisons.

An appropriate adjustment will be made for the stratification factor as described above, the blocking effect will be addressed through including the number of high-risk factors present (fixed effect) and GP practice (random effect).

There are 8 secondary outcomes. The most conservative approach would be to use Bonferroni $p=0.05/8=0.00625$ or a family-wise error rate of $\alpha=0.0065$ (so $1-(1-\alpha)^8 = 0.05$). A less conservative approach would be to take $p=0.01$ for significance of the secondary outcomes and this was agreed as appropriate at the TSC meeting of 9 September 2016.

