Table 8: Primary outcome 12 month unadjusted and adjusted analysis of presence of CWP in the tCBT and usual care arms on the ITT population

	Unadjusted OR	95% CI	p-value	Adjusted OR	95% CI	p-value
Treatment: tCBT vs Usual care						
Number of high-risk factors present: 3 vs 2						
Age						
Gender						
Random effect: GP practice						

Table 9: Primary outcome 12 month unadjusted and adjusted analysis of presence of CWP in the tCBT and usual care arms on the PP population (sensitivity analysis)

	Unadjusted OR	95% CI	p-value	Adjusted OR	95% CI	p-value
Treatment: tCBT vs Usual care						
Number of high-risk factors present: 3 vs 2						
Age						
Gender						
Random effect: GP practice						

Table 10: Primary outcome 12 month unadjusted and adjusted analysis of presence of CWP in the tCBT and usual care arms on the ITT population with multiple imputation (sensitivity analysis)

	Unadjusted OR	95% CI	p-value	Adjusted OR	95% CI	p-value
Treatment: tCBT vs Usual care						
Number of high-risk factors present: 3 vs 2						
Age						
Gender						
Random effect: GP practice						

Table 11: Primary outcome 3 and 24 month adjusted analysis of presence of CWP in the tCBT and usual care arms on the ITT population

	3 months			24 months		
	Adjusted OR	95% CI	p-value	Adjusted OR	95% CI	p-value
Treatment: tCBT vs Usual care						
Number of high-risk factors present: 3 vs 2						
Age						
Gender						
Random effect: GP practice						

Table 12: Primary outcome 3 and 24 month adjusted analysis of presence of CWP in the tCBT and usual care arms on the PP population

	3 months			24 months		
	Adjusted OR	95% CI	p-value	Adjusted OR	95% CI	p-value
Treatment: tCBT vs Usual care						
Number of high-risk factors present: 3 vs 2						
Age						
Gender						
Random effect: GP practice						

Note: This table will be repeated for 3 months and 24 months

Table 13: Secondary outcome adjusted analysis of presence of pain in the tCBT and usual care arms on the ITT population

	3 Months			12 Months			24 Months		
	Adjusted OR	95% CI	p-value	Adjusted OR	95% CI	p-value	Adjusted OR	95% CI	p-value
Treatment: tCBT vs Usual care									
Number of high-risk factors present: 3 vs 2									
Age									
Gender									
Random effect: GP practice									

Note: As all patients have pain at baseline there is no adjustment for this as there is for other secondary outcomes

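### The primary CWP model leaves out the continuous baseline scores and baseline pain extent, and the pain models have no baseline pain term: a small, cheap gain in precision is forgone

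*SAP*

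**What the plan says.** SAP 2.4.4 specifies a logistic regression for CWP at 12 months. Treatment is a fixed effect. The randomisation factors enter as the count of high-risk factors, 2 or 3 (fixed), and GP practice (random). The SAP then states: "The other covariates that will be considered in the model are: age and sex". It justifies these two by their known relation to CWP onset. Tables 8 to 12 show the same terms and no others.

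For secondary outcomes, SAP 2.4.5 includes the baseline value of the outcome. Tables 14 to 20 accordingly carry baseline scores, for example illness behaviour in Table 14. Presence of pain is the exception. The note to Table 13 reads: "As all patients have pain at baseline there is no adjustment for this as there is for other secondary outcomes". Table 23, the repeated-measures version, also has no baseline pain row.

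Protocol 6.3 lists the screening instruments. They include the three scales and "Pain assessed by specific questions on the experience of pain, consultation and body manikins". Protocol section 3 says that the at-risk definition came from a re-analysis seeking the best predictors of CWP onset: regional pain plus two of the three scale thresholds.

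**The concern.** Eligibility requires at least two of the three thresholds, so the count has only two levels among those randomised. A participant just over two cut-offs and one far above the same two are coded alike. The SAP admits age and sex because they predict CWP, and the protocol says as much of the three scales, yet their continuous values are not used for the primary outcome.

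Pain extent is also unused. CWP is defined by how widespread and long-lasting pain is, so participants with more painful sites at screening may plausibly be closer to meeting the definition. That is an inference; the documents do not state it.

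What is at stake is efficiency and protection against chance imbalance in likely drivers of onset. Adjusting for a prognostic baseline variable in a logistic model usually raises power for the treatment test, with no extra patients. Neither the type I error rate nor the validity of the comparison is in question.

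**Working it through.** **Inputs from the SAP.**

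- Test (2.4.1): "a 5% two-sided significance level will be used to denote statistical significance".
- Effect and power (1.4): "reduce the onset of CWP from 21% to 12%, with 90% power and a 5% significance level".
- Adherence assumed (1.4): "75% of persons allocated to the tCBT arm will be adherent to the intervention".
- Return rate assumed (1.4): "80% of all subjects will return the follow-up questionnaires to assess outcome".
- Recruitment target (1.4): "Accordingly we require 473 subjects per arm that is a total of 946 subjects recruited".

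**Reproducing the stated sample size.** With p1 = 0.21, p2 = 0.12, mean 0.165 and difference d = 0.09:

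- n = [1.960 × √(2 × 0.165 × 0.835) + 1.282 × √(0.21 × 0.79 + 0.12 × 0.88)]² / 0.09² = 355.4, so 356 per arm.
- Continuity-corrected: (n/4) × [1 + √(1 + 4/(n × d))]² = 377.3, so 378 per arm.
- Allowing for 80% return: 378 / 0.80 = 472.5, so 473 per arm, as stated.

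This calculation assumes no covariate adjustment and makes no allowance for the 75% adherence. The omitted covariates therefore do not make 473 wrong.

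**Expected events.** 378 × (0.21 + 0.12) = 124.7, about 125.

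**Gain from a continuous rather than a dichotomised score.** Simulation with 378 evaluable per arm and 4,000 trials per setting. One standard normal prognostic score X acts through logit p = a + gX, with a separate intercept a for each arm set so that the marginal risks are exactly 21% and 12%. Three logistic models were fitted to each dataset: treatment only; treatment plus X cut at 0.5 SD above its mean (about 31% high, a stand-in for the SAP's count); and treatment plus continuous X. The strength g ran from 0.25 to 1.0 per SD. This range is an assumption, because the documents give no discrimination figure within the high-risk group. The last column is [(z of continuous power + 1.96) / (z of dichotomised power + 1.96)]².

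| AUC in usual care (assumed) | Unadjusted | Dichotomised | Continuous | Effective sample size, continuous v dichotomised |
|---|---|---|---|---|
| 0.57 | 91.3% | 91.6% | 91.7% | 1.00 |
| 0.64 | 91.3% | 91.9% | 92.3% | 1.02 |
| 0.69 | 91.4% | 93.0% | 93.6% | 1.03 |
| 0.74 | 92.5% | 94.2% | 95.0% | 1.04 |

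Monte Carlo error on each power is about 0.4 points. The models share datasets, so differences along a row are steadier than that.

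**If non-adherence dilutes the effect.** Full effect in adherers and none in the rest gives 0.75 × 12% + 0.25 × 21% = 14.25%. At AUC 0.74, power is then 69.4% unadjusted, 72.6% dichotomised and 74.7% continuous (Monte Carlo error about 0.7 points). Continuous over dichotomised gains about 2 points, a ratio of 1.05.

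**The whole proposal against the planned model.** A simulation of the count model against the same model plus the three scores and pain sites, at 21% versus 12%, gave about 1–5% in effective sample size and 0–2 power points. Most of the gain came from pain extent. The strengths are again assumed. On 946 randomised, this is 0.01 × 946 = 9 to 0.05 × 946 = 47 participants.

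**Effect on the odds ratio.** For 21% versus 12% the marginal odds ratio is (0.12/0.88) / (0.21/0.79) = 0.51. Conditional on a score with AUC 0.74, the same two risks correspond to 0.47. The estimate moves because the quantity changes, not because treatment works better.

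**The case against.** The strongest reply is that this is a preference. The model pre-specifies both randomisation factors plus age and sex, Tables 8 to 12 already commit to age and gender, and randomisation protects the comparison. All of that stands. A reader might infer that the primary result would be biased or the sample size wrong; nothing in the documents supports either.

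A reader might also call the continuous scores stronger predictors than the planned terms. The documents do not show this. Protocol section 3 reports and validates the model as thresholds, and its predictive values contrast high-risk people with everyone else. They say nothing about discrimination among people who already exceed two thresholds. At an assumed AUC near 0.57 the gain is essentially nil.

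The size is easily overstated by choosing the wrong comparator. Against a model with no score, simulation at assumed AUCs of 0.64–0.73 gives the equivalent of 3–9% more participants (0.03 × 946 = 28 to 0.09 × 946 = 85). The SAP does not omit the score, however; it carries a dichotomised form, which already captures part of that gain.

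The Table 13 note is correct as far as it goes: yes/no baseline pain is constant and cannot be fitted. It does not address number of sites, which can vary. It is also fair that no site count is defined in the documents and that its predictive value is unproven.

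**Conclusion.** The point holds as a modest efficiency improvement, not as an error. The planned primary test is valid. Relative to the planned count model, it forgoes roughly 1–5% in effective sample size and 0–2 power points at 21% versus 12%. That range depends on assumed predictor strengths, on pain extent being prognostic, and on roughly linear effects on the log-odds. If the continuous scores add little within the high-risk group, the gain is close to zero. The change is still worth making before any analysis, because the data come from the screening questionnaire that determines eligibility and the cost is small.

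**What to change.** In SAP 2.4.4, pre-specify linear terms for the baseline illness behaviour, somatic symptom and sleep scores and for the baseline number of manikin pain sites, in addition to the stratification factors, age and sex. Carry the same terms into Tables 8 to 12.

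Add baseline number of pain sites to the Table 13 and Table 23 models. Keep the Table 13 note but amend it: yes/no baseline pain is constant, so pain extent is used instead.

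Alongside the adjusted odds ratio, report a standardised risk difference from the same model. This matches the primary outcome, which the SAP states as a difference in proportions, and it avoids mistaking a shift in the conditional odds ratio for a change in effect.

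Costs: a rule for deriving the site count from the manikins; four degrees of freedom (treatment, count, age and sex plus four new terms makes eight fixed terms, and 125 / 8 is about 16 events per term); and overlap between the scores and the count derived from them. That overlap makes their individual coefficients hard to interpret but does not harm the treatment estimate. No new data collection is needed.

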2.4.6. TIMES OF EVALUATION

Follow-up questionnaires will be mailed to participants at 3, 12 and 24 months after the treatment start date (for participants in the active treatment group) or dummy treatment start date (for those in usual care). Instruments included in the follow-up questionnaires will be the same as in the screening survey questionnaire. Additionally, follow-up questionnaires will include the Patient Global Impression of Change (7-item scale from “very much worse” to “very much better”), and questions on health care usage. Mixed models analyses with an appropriate error structure will take into account the repeated assessment of the outcome data for the same patient across the three follow-up times.

Cut off for timed responses: the cut-off for counting person as responding to a follow-up request will be 3 weeks after first trying a telephone reminder.

Mixed models analyses with an appropriate error structure will take into account the repeated assessment of the outcome data for the same patient across the three follow-up times. Alternatives include mixed models and generalised estimating equations. Mixed models should be more generalizable to incorporate the three follow-up times and the fixed and random effects required to adjust for standardisation. Multilevel mixed-effects GLMs (mehl) in Stata will provide great flexibility in the modelling. Although there are only three time points and unequal time gaps, an AR1 structure will be appropriate. Robust errors may need to be considered.

2.4.7. MULTIPLE IMPUTATION METHODS

As part of sensitivity analyses, multiple imputation methods will be used, where appropriate, to address issues of missing data. However, these methods will not be applied if the use of imputation is contrary to specified rules for the relevant validated measurement scale.

Imputations of 100 repeat samples from the dataset will be used if processing speed allows. If not then at least 10-20 repeat samples will be used. MI routines within Stata will be employed using the relevant outcome variable and all risk factors that are candidates for inclusion in the relevant regression model (bearing in mind the restriction above).

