2. ANALYSIS

2.1. STUDY POPULATIONS

Comparison between arms will be on an intention-to-treat basis (main analysis) with a per protocol sensitivity analysis.

Intention to treat (ITT) population

Intention to treat analysis will be of all participants who were randomised and for whom at least one follow-up observation of the primary outcome is available. Participants will be analysed in the group to which they were randomised.

[figure not shown]
Per protocol (PP) population

Pre protocol analysis will be of all participants of the ITT population excluding participants who were not compliant with their randomised study arm. Non-compliance is defined as those not having any primary outcome data and/or those not completing treatment as in the definition below.

Full intervention will consist of an initial assessment (45-60 minutes), 6 weekly sessions (each 30-45 minutes) over six weeks, and then booster sessions at 3 and 6 months. The per protocol analysis will be those receiving the completed treatment (defined below) vs. all others.

A participant in the CBT group has completed treatment if: there is mutual agreement between therapist and participant to stop treatment AND at least one session (the initial assessment) has been attended; OR, participant has at least 3 sessions of CBT (including the initial assessment)

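### As specified, multiple imputation of 12-month CWP returns the complete-case adjusted odds ratio, so Table 10 cannot test its sensitivity to missing data

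*SAP*

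**What the plan says.** SAP 2.4.4 sets the primary model: "The model for outcome CWP (yes or no at 12 months) will be a multiple logistic regression". Its terms are treatment, the number of high-risk factors and GP practice (a random effect), and then: "The other covariates that will be considered in the model are: age and sex". The same section continues: "Multiple imputation (MI) analysis will be used to examine sensitivity to missing data".

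The only statement of what enters the imputation is in SAP 2.4.7: the Stata routines will be run "using the relevant outcome variable and all risk factors that are candidates for inclusion in the relevant regression model", with 100 imputations or, failing that, at least 10 to 20. No auxiliary variable is named, and no analysis under a missing-not-at-random assumption is planned.

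SAP 2.1 defines the ITT set as "all participants who were randomised and for whom at least one follow-up observation of the primary outcome is available". Table 11 is titled "Primary outcome 3 and 24 month adjusted analysis of presence of CWP", so the SAP counts CWP at 3 and 24 months as observations of the primary outcome. Table 10 repeats the rows of Table 8 with imputation added. SAP 2.4.1 also says that "all comparative analysis will be conducted on an ITT mixed model basis", and SAP 2.4.6 with Table 22 plans a separate three-visit model for CWP.

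**The concern.** An imputation analysis can tell us something about missing outcomes only if it uses information that the main analysis does not, or changes the assumption about the missing values. The stated rule does neither. Table 10 will match Table 8 even if Table 8 is biased, and readers may take the match as reassurance.

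At the planned 80% return, about 189 of 946 outcomes will be missing at 12 months, in a trial where only one arm has contact with therapists. The ITT definition sharpens the point. If CWP at any visit counts, everyone imputed in Table 10 has CWP recorded at 3 or 24 months, and the rule names neither. If only 12-month CWP counts, nobody is left to impute.

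**Working it through.** **Size of the problem (SAP 1.4).** For 21% v 12%, 90% power and two-sided 5%, with mean proportion 0.165:

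n = [1.960 × √(2 × 0.165 × 0.835) + 1.2816 × √(0.21 × 0.79 + 0.12 × 0.88)]² / 0.09² = 356 per arm.

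The continuity correction gives (356/4) × [1 + √(1 + 4/(356 × 0.09))]² = 378, and 378/0.80 = 473, the SAP's figure. Expected missing: 0.20 × 946 = 189. Expected observed events: 378 × 0.21 = 79 and 378 × 0.12 = 45, in total 124.

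**Which variables can be missing.** Arm is assigned. Number of high-risk factors and practice are needed to randomise (Protocol 6.5). Age is an eligibility criterion (Protocol 6.3). Sex is assumed complete. That leaves 12-month CWP.

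**Why the rule returns Table 8.** With imputed values y*, the score for the logistic model is Σ(observed) x(y − p) + Σ(missing) x(y* − p). At the complete-case estimate the first sum is zero. Each y* is drawn from the same model fitted to the same observed cases, so it averages p and the second sum averages zero. What remains is Monte Carlo error.

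A simulation (946 participants, drop-out depending on 3-month CWP and arm) confirms this. The SD of the difference in log odds ratio, imputed minus complete case, was 0.021 with 20 imputations, 0.009 with 100 and 0.003 with 1000. The mean difference was never more than 0.001 in size. With 100 imputations the standard errors were 0.2198 (complete case) and 0.2202 (imputed). With practice as fixed effects the mean was 0.000 and the SD 0.012.

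**What Table 10 could miss.** The documents give no rates for this, so these are assumptions: 3-month CWP 14.8%; 12-month risk 58% with it and 15% without (0.148 × 0.58 + 0.852 × 0.15 = 21.4%); 24-month CWP 22%; practice SD 0.2 on the logit scale; 3-month CWP missing in 10% of 12-month responders; 24-month CWP missing in 15% of 12-month responders and 60% of non-responders. Let q be the share of 12-month non-responders who also lack 3-month CWP.

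The extreme can be checked by hand for no treatment effect and q = 0. Suppose tCBT drop-out is 45% with and 15.7% without 3-month CWP (0.148 × 0.45 + 0.852 × 0.157 = 20%), and usual care loses 20% at random. Observed tCBT risk is (0.148 × 0.55 × 0.58 + 0.852 × 0.843 × 0.15)/0.7996 = 0.194, odds 0.240. Full-data odds are 0.2136/0.7864 = 0.272. The ratio is 0.885, close to the simulated 0.884.

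Simulated ratio of odds ratios to full data (500 null trials per row, Monte Carlo SE about 0.004). The last column imputes CWP at all three visits by lean chained equations:

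| Drop-out with v without 3-month CWP | q | Complete case | As written | Three-visit imputation |
|---|---|---|---|---|
| Both arms 30% v 18.3% | 50% | 0.994 | 0.994 | 0.996 |
| tCBT only 30% v 18.3% | 0% | 0.950 | 0.951 | 0.995 |
| tCBT only 30% v 18.3% | 50% | 0.957 | 0.957 | 0.984 |
| tCBT only 30% v 18.3% | 75% | 0.954 | 0.954 | 0.970 |
| tCBT only 45% v 15.7% | 0% | 0.884 | 0.884 | 0.993 |
| tCBT only 45% v 15.7% | 50% | 0.888 | 0.888 | 0.956 |
| tCBT only 45% v 15.7% | 75% | 0.883 | 0.883 | 0.924 |
| Usual care only 45% v 15.7% | 50% | 1.122 | 1.122 | 1.044 |

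In the worst case, ln 0.884 = −0.123, and 0.123/0.18 is about two-thirds of a standard error. In log odds ratio, the mean absolute gap between imputation as written and complete case was 0.005 to 0.007 with 100 imputations and 0.011 to 0.014 with 20. The three-visit imputation moved 0.03 to 0.12 from complete case. In the tCBT-only extreme it removed 1 − ln 0.993/ln 0.884 = 94% of the bias at q 0%, 62% at q 50% and 37% at q 75%.

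A further run had practice as fixed effects and the three baseline scores in the imputation. In the same column order it gave 0.876/0.875/0.989 at q 0% and 0.889/0.889/0.952 at q 50%.

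**The case against.** The strongest reply is that SAP 2.4.7 is open-ended: it does not say that only these variables may be used, and SAP 2.4.9 uses the term risk variables for the symptom, illness behaviour and sleep scores. The text indeed forbids nothing. But it names no other input, SAP 2.4.4 lists only age and sex as further covariates, and adding the three baseline scores would still leave out CWP at 3 and 24 months. Auxiliary variables chosen after the data are seen are not pre-specified.

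Second, the three-visit mixed model does use early CWP. That mitigates the gap. However, Table 22 has a single treatment row, the meaning of its two time-interval rows is not stated, and the shell does not clearly give a 12-month odds ratio. The dummy tables are described as examples, so this could be settled by a clarification.

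Third, the bias is small or absent unless drop-out depends on early CWP differently by arm, and nothing in the documents shows that it will. Moderate one-arm drop-out gives 0.950 to 0.957, about a quarter of a standard error. Fewer than 189 people may be affected, since those with no CWP at any visit leave the ITT set: 132 are imputed at q 50% and 105 at q 75%. All of this stands and limits the importance of the point.

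Fourth, the random practice intercept was not fitted in the checks; practice was omitted or entered as fixed effects. Handling practice differently in imputation and analysis could produce a small difference, but one that says nothing about missing data. Leaving treatment out of the imputation would also separate the tables, but only by diluting the effect (odds ratio 0.624 v 0.551 with drop-out at random).

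**Conclusion.** The concern holds for the adjusted 12-month odds ratio. Followed as written, the imputation rule reproduces the complete-case estimate, with no change in bias and no gain in precision. This does not depend on the drop-out rates. It rests on complete model covariates and on treatment being part of the imputation model.

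The size of the bias that would go unseen does depend on assumed rates: negligible with similar drop-out in both arms, about 5% in the odds ratio in the moderate one-arm case, and about 12% in the extreme. The point does not cover the unadjusted column of Table 10, which can move slightly, or secondary outcomes with missing baseline scores. It should be corrected, but it does not undermine the primary analysis.

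**What to change.** In SAP 2.4.7, for the primary outcome, specify chained equations that impute CWP at 3, 12 and 24 months jointly. Each visit's model should contain arm, number of high-risk factors, age, sex, CWP at the other two visits, the interactions of arm with those two, and the baseline illness behaviour, somatic symptom and sleep scores. With the intercept this is 1 + 4 + 2 + 2 + 3 = 12 parameters, for about 124 observed 12-month events.

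Do not use fully separate models by arm with practice indicators and many scores. At the planned event rates such a model pulled the odds ratio towards the null (0.495 v 0.485 in full data with equal drop-out), while the lean model gave 0.486. Leaving practice out of the imputation cost nothing visible (0.958 v 0.956 in the extreme at q 50%). If practice is included, use an augmented or penalised fit to guard against perfect prediction.

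The SAP should also state that the analysis assumes missing at random, that it gains less where 3-month CWP is missing too, and that the report will give the number of imputed participants with CWP known at 3 months, 24 months or both. If the three-visit mixed model was the intended regression model, say so and report its 12-month odds ratio. Extending to all randomised participants and adding a delta-adjusted analysis are optional; only the latter would test departures from missing at random.

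The cost is one SAP paragraph and some extra analysis work. The variables are already collected (Protocol 6.3 and 6.6), and the analysis model and sample size do not change.
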